#### Roles and responsibilities in this study:

As co-investigator, [name] will assist in overseeing participant recruitment, data collection, and implementation of the intervention program. [name] will also assist in analyzing data, reporting data at conferences, and writing manuscripts for publication.

CITI Training Completed:  Social & Behavioral Researchers  Biomedical Researchers

5. Do you have additional research personnel (Co-Investigators, key personnel, student research assistants, etc.)?

NO  
 YES

To list additional investigators and/or key personnel, complete and attach an [ADDITIONAL PERSONNEL](#) form.

6. Is this research supported in whole or in part by a grant or contract?

NO  
 YES:

Sponsor Name:	National Institute on Alcohol Abuse and Alcoholism	
PI on Grant:	[name]	
Grant Title/Contract:	Efficacy of a Web-Based Alcohol Intervention for High School Students	
Project Period:	From: 7/1/2017	To: 6/30/2019
 Grant Project Summary Attached		
OSP Proposal Number (if known): this grant is pending - it has received a score in funding range - IRB required for JIT information for Advisor Council meeting in May 2017		

7. Has this protocol previously been considered by Boise State University's IRB?

NO  
 YES: IRB Number: \_\_\_\_\_ Date Approved: \_\_\_\_\_

## SECTION B: Financial Conflict of Interest Disclosure

*Conflicts of interest must be disclosed in accordance with the Boise State Conflict of Interest and Commitment [Policy #1110](#).*

1. Do any investigators (PI, Co-Investigator) or research team members (key personnel) have any relationship or equity interest with any institutions or sponsors related to this research that might present or appear to present a conflict of interest with regard to the outcome of the research?

NO POTENTIAL CONFLICTS EXIST  
 YES:

2. Name of the person(s) with the potential COI: \_\_\_\_\_

This potential conflict has been disclosed to the Boise State Conflict of Interest Office via the electronic disclosure form: <https://web.boisestate.edu/conflictofinterest/app.html>.  
 This conflict has not been disclosed to the Boise State COI Office.

**Note: If a significant conflict of interest exists, you must also attach the Boise State COI Committee approved management plan.** If you have questions about conflicts of interest, contact the Boise State Conflict of Interest Officer at [contact].

 **FULL BOARD Review:**

Any research or training project involving the use of human participants which does not fall into an exempt or expedited review category must be submitted for full board IRB review. Research involving more than minimal risk requires full board review.

 **EXPEDITED Review** (Indicate [category](#)(ies) below):

	1. Clinical studies of drugs and medical devices only when condition (a) or (b) is met.	
	 a.	research on drugs for which an investigational new drug application (21 CFR Part 312) is not required. (Note: Research on marketed drugs that significantly increases the risks or decreases the acceptability of the risks associated with the use of the product is not eligible for expedited review).
	 b.	research on medical devices for which (i) an investigational device exemption application (21 CFR Part 812) is not required; or (ii) the medical device cleared/approved for marketing and the medical device is being used in accordance with its cleared/approved labeling.
	2. Collection of blood samples by finger stick, heel stick, ear stick, or venipuncture as follows:	
	 a.	from healthy, nonpregnant adults who weigh at least 110 pounds. For these participants, the amounts drawn may not exceed 550 ml in an 8 week period and collection may not occur more frequently than 2 times per week; or
	 b.	from other adults and children  considering the age, weight, and health of the participants, the collection procedure, the amount of blood to be collected, and the frequency with which it will be collected. For these participants, the amount drawn may not exceed the lesser of 50 ml or 3 ml per kg in an 8 week period and collection may not occur more frequently than 2 times per week.
	3. Prospective collection of biological specimens for research purposes by noninvasive means.	
	Examples: (a) hair and nail clippings in a nondisfiguring manner; (b) deciduous teeth at time of exfoliation or if routine patient care indicates a need for extraction; (c) permanent teeth if routine patient care indicates a need for extraction; (d) excreta and external secretions (including sweat); (e) uncannulated saliva collected either in an unstimulated fashion or stimulated by chewing gumbase or wax or by applying a dilute citric solution to the tongue; (f) placenta removed at delivery; (g) amniotic fluid obtained at the time of rupture of the membrane prior to or during labor; (h) supra- and subgingival dental plaque and calculus, provided the collection procedure is not more invasive than routine prophylactic scaling of the teeth and the process is accomplished in accordance with accepted prophylactic techniques; (i) mucosal and skin cells collected by buccal scraping or swab, skin swab, or mouth washings; (j) sputum collected after saline mist nebulization.	
	4. Collection of data through noninvasive procedures (not involving general anesthesia or sedation) routinely employed in clinical practice, excluding procedures involving x-rays or microwaves. Where medical devices are employed, they must be cleared/approved for marketing. (Studies intended to evaluate the safety and effectiveness of the medical device are not generally eligible for expedited review, including studies of cleared medical devices for new indications.)	
	Examples: (a) physical sensors that are applied either to the surface of the body or at a distance and do not involve input of significant amounts of energy into the subject or an invasion of the subject's privacy; (b) weighing or testing sensory acuity; (c) magnetic resonance imaging; (d) electrocardiography, electroencephalography, thermography, detection of naturally occurring radioactivity, electroretinography, ultrasound, diagnostic infrared imaging, doppler blood flow, and echocardiography; (e) moderate exercise, muscular strength testing where appropriate given the age, weight, and health of the individual.	
	5. Research involving materials (data, documents, records, or specimens) that have been collected, or will	

	be collected solely for nonresearch purposes (such as medical treatment or diagnosis). (NOTE: Some research in this category may be exempt from the HHS regulations for the protection of human participants. 45 CFR 46.101(b)(4) . This listing refers only to research that is not exempt.)						
	6. Collection of data from voice, video, digital, or image recordings made for research purposes.						
	7. Research on individual or group characteristics or behavior (including, but not limited to, research on perception, cognition, motivation, identity, language, communication, cultural beliefs or practices, and social behavior) or research employing survey, interview, oral history, focus group, program evaluation, human factors evaluation, or quality assurance methodologies. (NOTE: Some research in this category may be exempt from the HHS regulations for the protection of human participants. 45 CFR 46.101(b)(2) and (b)(3). This listing refers only to research that is not exempt.)						
	8. Continuing review of research previously approved by the convened IRB as follows:						
	
 
 	a. where (i) the research is permanently closed to the enrollment of new participants; (ii) all participants have completed all research-related interventions; and (iii) the research remains active only for long-term follow-up participants; or	
 
 	b. where no participants have been enrolled and no additional risks have been identified; or	
 
 	c. where the remaining research activities are limited to data analysis.	
 
		a. where (i) the research is permanently closed to the enrollment of new participants; (ii) all participants have completed all research-related interventions; and (iii) the research remains active only for long-term follow-up participants; or		b. where no participants have been enrolled and no additional risks have been identified; or		c. where the remaining research activities are limited to data analysis.
	a. where (i) the research is permanently closed to the enrollment of new participants; (ii) all participants have completed all research-related interventions; and (iii) the research remains active only for long-term follow-up participants; or						
	b. where no participants have been enrolled and no additional risks have been identified; or						
	c. where the remaining research activities are limited to data analysis.						
	9. Continuing review of research, not conducted under an investigational new drug application or investigational device exemption where categories two (2) through eight (8) do not apply but the IRB has determined and documented at a convened meeting that the research involves no greater than minimal risk and no additional risks have been identified.						

#### SECTION E: Purpose

- Provide a summary of the purpose of your project. Include information about the background and rationale for the study and goal(s) of the proposed study. Use language understood by a person unfamiliar with this area of research. Specific jargon should be avoided or explicitly explained.

Underage drinking and the negative associated consequences represent a significant problem in the United States. Drinking in adolescence significantly increases the risk for developing alcohol dependence and heavy drinking in high school is associated with multiple negative interpersonal, academic, legal, and neurocognitive consequences. A significant body of literature supports the use of brief interventions based on social norming theory and motivational enhancement models to reduce heavy drinking and the associated consequences among college students. Recent reviews of the literature also indicate brief interventions are effective when delivered in a web-based format. In spite of the compelling need to provide alcohol interventions to high school students, application of evidence-based interventions is limited. Further research examining the efficacy of brief interventions delivered to seniors through the high school curriculum is warranted. The proposed project will address this gap by examining the efficacy of a web-based intervention for this high school age group.

The goal of this study is to reduce underage drinking. This study builds upon research conducted over the past five years in the school district. We evaluated the efficacy of a web-based intervention, eCHECKUP TO GO (San Diego State University Research Foundation, n.d), shown to be effective with college students (Doumas, Kane, 2011; Doumas, Workman, Smith, 2011; Doumas, Workman, Navarro, 2011; Doumas, Haustveit, 2010; Doumas, Anderson, 2009). Results of this evaluation with 9th grade students were promising, but results were not sustained over time. Because high school seniors' drinking patterns are more similar to those of college students than 9th grade students, this approach may be more useful with high school seniors. We evaluated this hypothesis with pilot data collected in the Boise School District in 2015-2016. Results suggest that the eCHECKUP TO GO was effective in reducing risk factors associated with alcohol use (Doumas, Esp, Trull, & Shearer, 2017) and alcohol use (Doumas, Esp, Flay, & Bond, in press) at a short-term follow-up.

The proposed study extends the literature by examining the eCHECKUP TO GO with high school seniors over a longer follow-up period, as well as examining mediators and moderators of intervention effects. All 12th grade students at the two participating school sites will be given the opportunity to participate in the study. All participants will complete an assessment packet containing questionnaires including demographic

information, the quantity and frequency of their drinking, beliefs about both the quantity and frequency of their peers' drinking, alcohol beliefs and expectancies, problems associated with drinking, personality characteristics, and future goals (see attachment 1). Classrooms within the high school schools will be randomly assigned to the following groups: eCHECKUP TO GO and control group.

What is your research question? State your hypothesis.

**The project is designed to evaluate the following hypothesis:** Participants in the eCHECKUP TO GO intervention condition will report a reduction in their quantity of alcohol consumption and alcohol-related consequences relative to those in the control group. We are also interested in mechanisms of change (e.g. changes in estimates of peer drinking and/or drinking expectancies) and if this program is more effective for some students than others (e.g. gender, baseline drinking status, social-emotional maturity, college-bound status).

What will you do with the results of your study (e.g. contributing to generalizable knowledge, publishing, sharing at conference, etc.)? If this project is only for internal evaluation or to complete a class assignment, IRB may not be required. Please contact the ORC for additional information.

**Results of this study will be presented at conferences via oral or poster presentations and through publication in peer-reviewed journals. In addition a project summary report will be sent to the participating schools and/or school district.**

## SECTION F: Participant Population

1. Provide a description of the participant population you intend to recruit and collect data from. Describe the characteristics of the participant population such as gender, age ranges, ethnic background and health status, as applicable to the research.

**Participants (12th grade students; N = 1000) will be recruited from Capital High School and Boise High School in the Boise School District. All 12th grade students will be given the opportunity to participate in the study.**

**We anticipate the demographics to be as follows:**

47% male; 53% female

Ages 16-18

91% Caucasian, .03% African American, .05% Asian American, .002% Native American, .06 % Hispanic and .01% other

**We anticipate the student participants will be healthy.**

2. Will your research involve vulnerable populations, such as children or adolescents under the age of 18, pregnant women, prisoners or cognitively, economically, or educationally impaired participants?

NO  YES (indicate population): \_\_\_\_\_

If yes, describe additional safeguards planned to protect the rights and welfare of this population(s):

Student participants recruited to this research study will be approximately 1000 high school seniors (ages 16-18) from Capital High School and Boise High School in the Boise School District. Classrooms within the schools will be randomized to intervention or assessment-only control conditions. Participants will be recruited from classes. A letter will be sent by the schools to parents and their students prior to the study explaining the research. Parents will be asked to return consent forms using a self-addressed stamped postcard. Students will be invited to participate in the research study during class. Those students who decline participation will participate in an alternate academic activity under the supervision of the teacher. Consent procedures will be the same for minors and 18 year old students as the Boise School District requires parental consent for 18 year old students.

The surveys will ask student participants about their own alcohol use/non-use and any negative consequences, attitudes and beliefs about alcohol use, reasons for using alcohol use, norms for alcohol use, personality characteristics, future plans, and demographic information. Similar procedures have been used in previous research with 9th grade students and high school seniors without adverse incident. Psychological risks posed by the research are primarily related to the content of the assessment measures. Items include thoughts and feelings that may be private and personal behavior such as alcohol use. These questions may make participants uncomfortable, or be perceived as an intrusion on their privacy. Although it is important to consider these potential risks, and it is important to point out the potential for these risks, we have not observed any indications of these risks materializing in all of our previous research using procedures similar to those we will use in the proposed study.

All data and other information in this study will be maintained confidentially, but data will not be anonymous due to the longitudinal nature of participation. In order to protect against risks posed by the potential loss of confidentiality, we will take the following steps: 1) participants will be assured that they are free to refrain from answering any questions they do not wish to answer; 2) all data will be identified only by a unique personal identifier (PIN), which will be randomly generated for study purposes; 3) a master list of names and code numbers will be stored in locked file cabinets under the supervision of the PI and will be available only to research staff on this project. Data will be retained on computers with restricted and password protected access, without links to the master code list. All data based on this research will be reported in aggregate form.

3. Will you be recruiting students from a class that you teach? (See IRB [guidelines](#) for using your own students.)
 

NO  YES

If yes, explain why this population is necessary to the study, and how you will ensure participants do not feel coerced to participate. Coercion is a significant concern.
4. Will you be recruiting employees who report to you?
 

NO  YES

If yes, explain why this population is necessary to the study, and how you will ensure participants do not feel coerced to participate. Coercion is a significant concern.
5. Indicate any exclusion criteria for participants.  
**There are no exclusion criteria for recruitment other than not meeting inclusion criteria other than not being a senior at one of the two school sites.**
6. How many participants do you anticipate are needed for this research?  
**We anticipate a 45% response rate (students with parental active consent, student assent, and who are present the day of data collection) - this will yield 450 student participants in this study which will provide a large enough sample to adequately power this study.**

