#### SECTION G: Recruitment and Informed Consent

1. Attach copies of all applicable recruitment materials:
 

Recruitment Scripts (what will be said to participants during recruitment)  
 Recruitment Emails  
 Cover Letters  
 Flyers  
 Advertisements  
 Other:
2. Who will recruit potential participants?  
**We have recruited Capital High School and Boise High School in the Boise School District by contacting the principal. Participants will be recruited through the high schools from 12th grade classes. Student participants' names will be obtained from the registrar's list of seniors, which have the names, street addresses, and current phone numbers for all students. This information can be obtained directly from the registrar's computer database. Recruitment letters to parents will be sent directly from the school.**
3. Describe how, when, and where individuals will be first contacted about their interest in participating in the study (e.g., face-to-face, email, flyers, advertisements, phone call, etc.).  
**A pre-notification letter will be sent by the school to parents early in the academic year. A second letter will be sent explaining the study, include the consent form and a project-addressed stamped envelope for return of the consent form. A reminder letter and consent form with project-addressed stamped envelope will be sent to parents who do not return the initial consent form. All letters will be sent to parents' permanent addresses, provided to us via the registrar's office. Additionally, letters with consent form with a project-addressed stamped envelope will be sent home with students.**

Students with parental consent will be invited to participate in the research study during class. Students will be given an assent form which will address the voluntary nature of participation, participants' rights, the risks of participation, the availability of referral options outside the study for help with alcohol use prevention or treatment, data retention and storage information, protections for and limits to confidentiality, a description of the interventions, and procedures for reporting complaints and/or adverse events to the investigators and to the University Human Subjects Review Committee. Participants will be given a copy of the consent document. Students who elect not to participate will be given an alternative academic activity to complete under the supervision of the teacher during the assessment and intervention class periods.

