**Students will be invited to participate in the research study during class. Students will be given an assent form which will address the voluntary nature of participation, participants' rights, the risks of participation, the availability of referral options outside the study for help with alcohol use prevention or treatment, data retention and storage information, protections for and limits to confidentiality, a description of the interventions, and procedures for reporting complaints and/or adverse events to the investigators and to the University Human Subjects Review Committee. This will be presented by [name]. It will be clearly stated to the participants that participation is voluntary. Students who elect not to participate will be given an alternative activity to complete during the assessment and intervention class periods.**

10. Into what languages will the consent be translated? (*NOTE: Translated consent documents must be reviewed and approved by the IRB prior to use.*)

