**Applications missing this section will not be accepted.**

All student participants will be asked to complete an online survey during class time. This will take no longer than 20 minutes. Participants in the classrooms randomly assigned to the intervention group will be asked to complete an online intervention program which will occur during class time. The program involves a comprehensive assessment of the participant's drinking and drinking-related behaviors, followed by systematic personalized feedback to the participant about their alcohol use feedback in relation to their peer group. The program will take about 30 minutes to complete. Participants will then be asked to complete a brief exit survey regarding the intervention. Participants will be asked to complete the survey at 6 weeks and 6 months in the computer lab at their school. This survey will be completed online during class periods and will take no longer than 20 minutes to complete. Participants will also complete a very brief survey to assess help seeking. This will occur at the 6 week and 6 month follow-up assessments.

5. Where will the data collection and data analysis procedures take place? (i.e., explain where you are distributing surveys, conducting interviews, etc.)

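### Does the plan need a rule that a class's arm stays concealed until consent, assent and baseline are complete, and a rewording of the reward and coercion text?

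*Combined protocol and SAP*

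**What the plan says.** **Allocation.** Section E states: "Classrooms within the high school schools will be randomly assigned to the following groups: eCHECKUP TO GO and control group". It puts this after the assessment packet. Section F, item 2 mentions allocation first and recruitment second: "Classrooms within the schools will be randomized to intervention or assessment-only control conditions. Participants will be recruited from classes". Neither place gives a time for the allocation or for its disclosure.

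**Joining.** Under Section G, item 3, the school posts a pre-notification letter, a consent letter and a reminder to parents, and a further copy goes home with the student. After that, "Students with parental consent will be invited to participate in the research study during class". For those who decline, "Students who elect not to participate will be given an alternative academic activity to complete under the supervision of the teacher"; the same sentence refers to both assessment periods and intervention periods. Section G, item 9 adds: "It will be clearly stated to the participants that participation is voluntary".

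**Sessions.** Section H, item 4 gives every student an online survey of at most 20 minutes. Then "Participants in the classrooms randomly assigned to the intervention group will be asked to complete an online intervention program". On length: "The program will take about 30 minutes to complete". A brief exit survey follows.

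**Numbers and reward.** Section F, item 6 expects a "45% response rate (students with parental active consent, student assent, and who are present the day of data collection"), which it says yields 450 participants. Section H, item 7 offers the teacher a $100 certificate for classroom supplies and the class a pizza party once the class response rate reaches 60%.

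**Coercion.** Section K, item 1 denies any risk of coercion on two grounds: an emailed invitation can be deleted, and a student can leave the study at any time.

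**Analysis.** The Statistical Analysis Plan fits treatment, time (baseline, 6 weeks, 6 months) and their interaction in a mixed model.

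**The concern.** Whole classes are randomised, but parents and students decide one by one whether to join. Randomisation protects the comparison only if those decisions do not depend on the arm. With 45% expected to join, there is room for the two arms to recruit different kinds of student if the arm is known beforehand. The timetable might give it away: if survey and program share a session, an intervention class needs about 50 minutes and a control class about 20. A difference in motivation to change, or in drinking trajectory, would pass straight into the treatment-by-time contrast.

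Two further points concern voluntariness rather than bias. On the usage in Section F, item 6, a student who says no does not count towards the reward, and the teacher who supervises decliners also receives the certificate. And the no-coercion statement leans partly on an email, although recruitment is described as letters plus an in-class invitation.

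**Working it through.** **1. The plan's own count.** 1000 seniors × 0.45 = 450, as stated. If eligible students split evenly (assumed, 500 per arm), 500 × 0.45 = 225 join in each arm.

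**2. Order of events.** Section E mentions assessment before assignment; Section F, item 2 mentions randomisation before recruitment; Section H, item 4 describes the baseline survey and then the program in classes already assigned. These are narrative orders, not a schedule, so they establish neither early nor late disclosure. Parental consent, the first gate, is sought by letters that start early in the academic year, with no arm-specific version described. One assent form is described, and it tells every student about the interventions.

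**3. Session length.** 20 + 30 = 50 minutes plus the exit survey, against 20 minutes, holds only if survey and program share a session. No section says they do. The reference in Section G to assessment periods and intervention periods is compatible with separate sessions, in which case the baseline booking need not differ by arm.

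**4. Size of a selection effect.** Every input except the 45% is assumed. Let joining be L lower in one arm.

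- *Those lost differ by d SD in change over time from the average would-be joiner.* Bias = L × d / (0.45 − L).
  - L = 0.02, d = 0.25: 0.005 / 0.43 = 0.012 SD.
  - L = 0.05, d = 0.5: 0.025 / 0.40 = 0.063 SD.
- *Those lost differ by 1 SD in the measured baseline score, with baseline to follow-up correlation r.* Bias = (1 − r) × L / (0.45 − L).
  - L = 0.02, r = 0.8: 0.2 × 0.0465 = 0.009 SD.
  - L = 0.05, r = 0.5: 0.5 × 0.125 = 0.063 SD.
- *Those lost differ by a stable level present at every visit.* Both time points shift equally, so the planned contrast has zero bias.

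For scale, take 225 per arm, unit SD at each visit, r = 0.5, and no clustering or dropout. The change score has variance 2 × (1 − 0.5) = 1, so the standard error of the contrast is √(2/225) = 0.094 SD. The worst case above is 0.063 / 0.094 = 0.67 of that. Positive within-class correlation and dropout would make the standard error larger.

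**5. What analysis can do.** In the second case, adjusting for the baseline score removes the bias: the follow-up means differ by r times the baseline difference, and the regression slope is r. In the third case the planned contrast is already right, and baseline adjustment would itself leave (1 − r) × L / (0.45 − L). Only selection on trajectory is beyond both analyses.

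**6. The reward threshold.** (60 − 45) / (100 − 45) = 15/55 = 27%. This does not measure pressure on students. The 45% also requires parental consent and attendance, so the other 55% includes absentees and students who were never invited. The 45% may also already allow for the reward. If each student joined independently with probability 0.45 (assumed), a class would reach 60% with probability 13%, 10%, 7% or 5% for assumed class sizes of 20, 25, 30 or 35.

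**7. The email.** Sections F and G describe postal letters, copies carried home and an in-class invitation. The first ground in Section K, item 1 does not match these. The second ground, freedom to stop at any time, does not depend on an email, and Section K, item 2 adds the right to refuse any portion.

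**The case for a change.** The strongest argument for a change is that class randomisation with individual consent is a setting where concealment matters, and one sentence would secure it. Selection on motivation cannot be recovered from the baseline score, and the worst case above is two thirds of an optimistic standard error, which is not trivial. The voluntariness points concern students aged 16 to 18 reporting potentially illegal behaviour, with a teacher who gains from a high count.

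Much of this is accurate. The timing of disclosure is unstated, Section H, item 7 does not define its response rate, and the email does not fit. It is also true that no planned analysis removes selection on trajectory.

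The step from there to a defect does not stand. No section sets a rule that reveals the arm early, and no figure in the documents suggests that joining would differ by arm. The 0.01 to 0.06 SD range comes entirely from assumed losses and differences. Nothing makes the reward differ by arm, so it gives no reason to expect bias in the contrast. Counting returned forms whatever the answer would fix the meaning of a term the plan leaves open, and might cost participation in exchange for less pressure. That is a trade-off for the investigators and the IRB, not an error to correct.

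**Conclusion.** No change to the plan follows. The three parts close for different reasons.

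- **Disclosure of the arm** is an operational gap that the study team can fill sensibly: finish consent, assent and baseline in a class before its arm is announced. The described procedures already permit this. Joining counts by arm can be reported without amending the plan. Any bias cannot be sized from the documents; under the assumed inputs it is 0.01 to 0.06 SD, and zero for a stable difference in level.
- **The reward** uses an undefined term, and on either reading it weighs participation against pressure. It does not alter the treatment comparison.
- **The email sentence** is a clerical slip. The right to stop at any time, stated in the same sentence, is unaffected.

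This rests on the supplied text. The recruitment scripts and the consent and assent forms were not available. If they showed the arm being announced before students decide, the first part would need to be reopened.
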